## **2.9 Randomisation**

### **2.9.1 Randomisation allocation concealment and blinding**

This is a non-randomised Phase 1 study with no comparator arm. Eligibility checks will be carried out by the team to ensure that potential participants meet eligibility criteria. Written consent for entry into the trial will be obtained before any salve is applied to the skin. It is not possible to blind participants or practitioners to group allocation due the garlic content in the salve.

### **2.9.2 Post-randomisation withdrawals and exclusions**

Participants may decline to continue involvement in the trial at any time, without prejudice.

**Follow up:** Core outcomes will be completed over the telephone, if postal copies are not returned. Text messages may also be sent to those participants, who have given their prior consent by initialling the corresponding box on the consent form and providing their mobile telephone number.

Reminders will be sent by text message or email if no contact is made after 48 hours. Paper CRFs containing identifiable data will be stored separately from CRFs that correspond to the participant by participant ID number only.

## **2.10 Trial treatments / intervention**

### **2.10.1 Trial treatment(s) / intervention**

After consent and recruitment, a small drop of the Bald's salve (intervention) will be applied onto a sticking plaster and applied to the participant's upper arm.

### **2.10.2 Compliance**

Follow-up will be after 48 hours. Anyone who we fail to contact after a maximum of ten days will be recorded as a loss to follow-up.

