## **1.8 Assessment and management of risk**

There will be some risk of experiencing skin redness or irritation from the skin patch test, arising either from application of the Bald's salve or from the sticking plaster. The products within the salve include garlic (active ingredient allicin), onion, wine and bovine bile. We do not anticipate any serious adverse events such as those resulting in death, hospitalisation, life threatening illness or permanent disability. Any participant experiencing any discomfort will be advised to remove the plaster and gently wash the area with soap and water. If symptoms persists, we advise them to visit their GP.

In light of Covid-19, there are also risks associated with contact between participants and the research team. We have taken steps to ensure rules regarding distancing and protection are adhered to. A Perspex sheet will be placed between the attending volunteer and researcher; facial masks will be worn by all personnel and participants. The Perspex sheet will be adapted to allow the participant's upper arm to be accessed for patch test application. Face to face assessment at 48 hours, as originally planned, has been replaced with telephone or video link contact. The study will be administered in keeping with WCTU SOPs for risk assessment and monitoring.

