## **2.4 Outcome measures**

### **2.4.1 Safety profile of ancientbiotic**

#### **Primary Outcome:**

Frequency (prevalence) and character of adverse events at 48 hours after application of 100 µl ancientbiotic on a sticking plaster applied to the upper arm.

**Follow-up:** No further follow-up beyond 48 hours. If there is no skin reaction within 48 hours, we do not anticipate any longer term adverse events. However the study email account will be kept open for up to three months and participants will be advised to contact us if any suspected later reaction occurs.

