## 3.2 ADVERSE EVENT MANAGEMENT

### 3.3 Definitions

#### 3.3.1 Adverse Events (AE)

An Adverse Event (AE) is defined as any untoward medical occurrence involving a participant, which does not necessarily have a causal relationship with the intervention or trial.

**Expected AEs**, related to the ancientbiotic intervention, may include:

- Skin redness
- Skin itchiness
- Skin discomfort

We will capture symptoms arising within and at 48 hours.

**Unexpected AEs** related to the ancientbiotic will be recorded via self-report by the participant up to 48 hours or at 48 hours when contacted by the research team.

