### **3.5 Responsibilities**

#### Co-Investigators:

1. Checking for AEs when participants attend for follow-up.
2. Using clinical judgement in assigning seriousness, causality and expectedness.
3. Ensuring that all SAEs are recorded and reported to the Sponsor within 24 hours of becoming aware of the event, and providing further follow-up information as soon as available.
4. Ensuring that AEs are recorded and reported to the Sponsor in line with the requirements of the protocol.

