## **5 STATISTICAL ANALYSIS**

### **5.1 Power and sample size**

No sample size was calculated for this phase 1 study. The aim is to assess safety of the salve. The primary outcome will be adverse skin effects over 48 hours e.g. redness, heat, swelling or other. Type, number (%) and spread/distribution will be recorded.

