### **5.2.6 Procedure(s) to account for missing or spurious data**

Whilst every effort will be made to ensure compliance and data collection, it is inevitable that some data will be missing. Careful monitoring of missingness will be conducted. We do not intend to use multiple imputation methods for this pilot trial. Some data may not be available due to voluntary withdrawal of participants, lack of completion of individual data items or general loss to follow-up. Where possible the reasons for data 'missingness' will be ascertained and reported. The nature and pattern of the missingness will be carefully considered, including whether data can be treated as missing completely at random.

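### The 48-hour primary outcome has no acceptance window although first contact may run to ten days, and the protocol gives conflicting modes for the assessment

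*Protocol*

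**What the plan says.** **Timing of the outcome.** Section 2.4.1 gives the primary outcome as "Frequency (prevalence) and character of adverse events at 48 hours after application of 100 µl ancientbiotic on a sticking plaster applied to the upper arm", and the Study Summary also places the assessment at 48 hours. Section 5.1 words it as a period: "The primary outcome will be adverse skin effects over 48 hours e.g. redness, heat, swelling or other". Section 3.3.1 covers both: "We will capture symptoms arising within and at 48 hours".

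**Latest contact.** Section 2.9.2 provides for reminders when no contact has been made after 48 hours. Section 2.10.2 sets the limit: "Anyone who we fail to contact after a maximum of ten days will be recorded as a loss to follow-up". It does not say whether the ten days start at application or at the 48-hour point. Exclusion criterion 6 (section 2.5.2) concerns being reachable within 48 hours of the intervention.

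**Mode.** Section 1.8 states "Face to face assessment at 48 hours, as originally planned, has been replaced with telephone or video link contact", and section 2.2 agrees, adding email. Section 2.9.2 states "Core outcomes will be completed over the telephone, if postal copies are not returned". Table 1 in section 3.1 heads the Day 2 column as a clinic visit. The co-investigators' duties in section 3.5 include "Checking for AEs when participants attend for follow-up".

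**Images and missing data.** Sections 1.6 and 2.2 limit photographs to volunteers reporting a reaction plus five without one. Section 5.2.6 rules out multiple imputation, plans to monitor missingness and report reasons where possible, and will consider its nature and pattern, "including whether data can be treated as missing completely at random".

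**The concern.** This is a single-arm safety study whose only result is a descriptive frequency, with the type and spread of the reactions. How and when the skin is assessed is therefore the whole measurement.

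There is no routine face-to-face examination at 48 hours. If the first contact comes a week later, the volunteer must remember whether a reaction occurred and when it began, and any photograph shows the skin as it is that day. A mild redness may have been forgotten or may have cleared. The protocol accepts such a report on the same terms as one made at 48 hours, and readers of the results could not tell the two apart.

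The conflicting modes add to this. A clinic inspection, a video view, a telephone answer and a postal form do not detect or describe a faint reaction equally well, and staff cannot follow all four instructions.

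**Working it through.** Section 5.1 says that no sample size was calculated, and the protocol gives no expected reaction rate, precision, late-contact rate or loss rate. There is no plan figure to reproduce. The rates in steps 3 and 5 are assumptions that show scale only.

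**1. How late can a 48-hour outcome be?** The outcome falls on day 2 and the contact limit is ten days.
- Counted from application: 10 − 2 = 8 days after the 48-hour point.
- Counted from the 48-hour point: 10 days after it, which is day 2 + 10 = 12 after application.

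**2. What does a late contact still supply?** On the wording of sections 5.1 and 3.3.1, a reaction that began within 48 hours and has since faded still counts and can still be reported. On the point wording of section 2.4.1 this is less clear. On either wording the volunteer must place the reaction in time from memory. Section 3.4 asks for start and end dates for serious adverse events. The protocol asks for no such dates for the ordinary skin reactions that form the primary outcome, and no date of assessment. The CRF itself is not shown and may hold them.

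**3. Size of the recall effect.** Let p be the true rate, g the share of volunteers first contacted late, and h the share of reactions missed when contact is late. Observed rate = p × (1 − g × h). With p = 10%:

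| g (late) | h (missed) | Observed rate |
|---|---|---|
| 10% | 50% | 10% × (1 − 0.05) = 9.5% |
| 30% | 50% | 10% × (1 − 0.15) = 8.5% |
| 50% | 50% | 10% × (1 − 0.25) = 7.5% |
| any | 0% | 10.0% |

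For comparison, the exact (Clopper-Pearson) 95% interval for 10/100 is 4.9% to 17.6%, so these shifts lie within sampling error. Type and spread are more exposed than the count, because they depend on seeing or describing the skin.

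**4. Mode of the 48-hour assessment, side by side.**

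| Place in the protocol | Mode |
|---|---|
| 1.8 and 2.2 | Telephone or video, with email; face to face withdrawn |
| 2.9.2 | Postal form first, telephone as fallback |
| 3.1, Table 1 | Clinic on Day 2 |
| 3.5, Co-Investigators | Participants attend |

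These cannot all be current. Sections 1.8 and 2.2 say that the face-to-face plan was replaced, so the remote mode appears to be the intended one.

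**5. Loss to follow-up, as supporting context.** Assume that 10 of 100 are never reached.
- With 5 reactions among the 90 reached: 5/90 = 5.6% (1.8% to 12.5%). With the 10 lost counted as no reaction: 5/100 = 5.0% (1.6% to 11.3%). With the 10 lost counted as reactions: 15/100 = 15.0% (8.6% to 23.5%).
- With no reactions among the 90: 0/90 has an upper limit of 4.0%. The opposite extreme is 10/100 = 10.0% (4.9% to 17.6%).

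The direction of bias is not fixed. Let the true rate be p = 10%, overall loss L = 10%, and let reactors be lost r times as often as non-reactors. The loss among non-reactors is L / (p × r + 1 − p), and the loss among reactors is r times that.
- r = 2: 0.10 / 1.10 = 9.09%, so reactors lose 18.18%. Observed rate = 10% × (1 − 0.1818) / 0.90 = 9.1%.
- r = 1: 10.0%.
- r = 0.5: 0.10 / 0.95 = 10.53%, so reactors lose 5.26%. Observed rate = 10% × (1 − 0.0526) / 0.90 = 10.5%.

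**The case against.** The strongest reply is that ten days limits how long staff chase a volunteer and is not the planned assessment time. Contact is planned after 48 hours, reminders follow, and sections 2.5.1 and 2.5.2 select people who can be reached. Longer chasing also reduces loss. Section 3.3.1 keeps any symptom arising within 48 hours reportable, section 2.2 asks for any sign of reaction, and section 1.6 gives volunteers an email address and telephone number to use straight away. On mode, sections 1.8 and 2.2 already show which one is current, so Table 1 and section 3.5 look like leftover wording.

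Much of this stands. It makes late contact less likely and leaves a faded reaction countable. It does not date a late report, restore an image of the skin at 48 hours, or say how late reports are shown. The leftover wording still has to be corrected, and the postal route in section 2.9.2 is a further inconsistency. An analysis plan cannot settle how the data are collected.

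A reader might also infer more than the text supports:
- *Volunteers never reached leave the denominator.* Section 2.10.2 only labels them lost. The protocol defines no denominator, and a SAP that is not shown may do so.
- *Faded reactions are scored as absent.* No section says so, and section 3.3.1 points the other way.
- *Missingness is examined only as missing completely at random.* Section 5.2.6 names that as one item within a wider look at nature and pattern, and does not assume it.
- *Loss lowers the rate.* It may raise it if people with a reaction are the more likely to respond.

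**Conclusion.** The point holds as a defect in how the only outcome is collected, in two parts. First, the 48-hour outcome has no acceptance window: a first contact 8 or 10 days after the 48-hour point, depending on an unstated origin, counts like any other, and the protocol requires no date of assessment or onset. Second, the mode of assessment is contradictory across five places and must be reconciled.

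The effect on the rate is probably modest. It is downward if late-contacted volunteers forget reactions and nil if they do not. The 9.5% to 7.5% against a true 10% rests on assumed shares contacted late and reactions missed. The larger risk is to the description of type and spread.

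Loss to follow-up is supporting context only. The case in which all 10 unreached volunteers reacted is an assumed extreme, not an expectation.

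**What to change.** 1. **Date the outcome.** Have each volunteer complete a short dated self-report form at 48 hours, handed out on Day 0 and returned electronically or read out at the remote contact. A late call then draws on a record made on time. Keep photographs to those with a reaction plus the five planned controls, as in sections 1.6 and 2.2. A photograph from everyone would go beyond the agreement sought in section 1.6 and in inclusion criterion 8.
2. **Define it once.** Record date and time of assessment and of onset on the CRF. Word the outcome in the Study Summary and in sections 2.4.1 and 5.1 as a reaction with onset within 48 hours. State when the ten days begin.
3. **Show late contacts.** Fix in advance what counts as late (for example, first contact after day 3) and give the rate with and without these volunteers.
4. **Use one mode.** Align Table 1 of section 3.1, section 2.9.2 and section 3.5 with the remote mode of sections 1.8 and 2.2.
5. **Optional.** Report the number lost beside the rate, with bounds counting them as no reaction and as reaction, and say that loss may bias the rate either way.

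The cost is small: protocol and CRF wording, one short form and a few table rows, with no new visits. Section 6.2 gives changes to outcomes as an example of a substantial amendment, so the reworded outcome may need ethics committee approval.

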## 2.11 Blinding and allocation concealment

As this is a non-randomised pilot safety study, we will not randomise participants. There will be no blinding of volunteers or research team. Due to the garlic content in the Bald's salve, it is currently not possible to blind participants to the intervention as the product is identifiable by smell.

## 2.12 Concomitant illness and medication

### 2.12.1 Concomitant illness

We will exclude any people with asthma, diabetes, skin conditions or anyone with allergies.

## 2.13 End of trial

The trial will end when data collection and statistical analysis has been completed. We will notify the relevant REC within 90 days of the end of the study.

# 3 METHODS AND ASSESSMENTS

## 3.1 Schedule of data collection

**Table 1. Trial visits/assessments**

Visit	WMS Clinic / Phone	WMS Clinic	WMS Clinic
Time-point	Pre-consent	Day 0	Day 2
Eligibility checks (in person or on phone)	X		
Written/verbal information about study	X		
Written informed consent	X	X	
Digital photograph image, if indicated			X
Skin check at baseline		X	
Outcome assessment			X
Any other adverse event		X	X

## 3.2 Long term follow-up

Not applicable. We do not anticipate any longer term adverse events beyond 48 hours. However, we will keep the resource email account open for a period of three months beyond the end of recruitment and advise participants they can contact the study team by email if any suspected adverse event occurs in the longer term.

## 3.2 ADVERSE EVENT MANAGEMENT

### 3.3 Definitions

#### 3.3.1 Adverse Events (AE)

An Adverse Event (AE) is defined as any untoward medical occurrence involving a participant, which does not necessarily have a causal relationship with the intervention or trial.

**Expected AEs**, related to the ancientbiotic intervention, may include:

- Skin redness
- Skin itchiness
- Skin discomfort

We will capture symptoms arising within and at 48 hours.

**Unexpected AEs** related to the ancientbiotic will be recorded via self-report by the participant up to 48 hours or at 48 hours when contacted by the research team.

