## STUDY SUMMARY

Trial Title	Assessment of safety of a medieval antibiotic to treat infected diabetic ulcers: a Phase 1 trial in healthy volunteers
Sponsor ref. number	
Clinical Phase	Phase I
Trial Design	Single centre non-randomised, uncontrolled intervention study
Trial Participants	Healthy volunteers, aged from 18 to 79 years
Planned sample size	100 participants
Treatment Duration	48 hours
Follow-up Duration	48 hours
Planned Trial Period	1 April 2021 to 1 July 2021 (3 months)
Objectives	
To aim is to determine the safety of an ‘ancientbiotic’ (Bald’s salve) when applied to the skin of human volunteers. The ancientbiotic is a mixture of natural products used in a historical infection remedy.
 
The specific objective is to determine the frequency of adverse events associated with a patch test of Bald’s salve applied to the skin of human volunteers.

Outcomes	
Primary	Skin irritation assessed at 48 hours.
Secondary	Any other adverse event associated with the patch test application of Bald’s salve.

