### 3.4 Reporting related and unexpected SAEs

All SAEs will be entered onto the appropriate reporting form and returned to WCTU. All SAE reports will be recorded within 24 hours of the investigator being made aware. The CI will compile all the necessary information. WCTU is responsible for reporting any related and unexpected SAEs to the sponsor and REC within required timelines. All SAEs will be recorded for inclusion in the annual reports to the REC. The CI and Cols will review causality.

The causality of SAEs (i.e. relationship to trial intervention) will be assessed by the investigator(s) using the SAE form (table 2).

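### Section 3.3.1 words the recording of unexpected adverse events as those related to the salve, against its own cause-neutral definition and the outcome, schedule and analysis sections

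*Protocol*

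**What the plan says.** Section 3.3.1 of the protocol defines an AE as an untoward medical occurrence that "does not necessarily have a causal relationship with the intervention or trial". It lists skin redness, itchiness and discomfort as expected AEs and adds: "We will capture symptoms arising within and at 48 hours". Its next sentence concerns unexpected AEs, which, if "related to the ancientbiotic will be recorded via self-report by the participant up to 48 hours", or at the 48-hour contact, enter the record.

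Elsewhere the scope is worded differently:

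- Section 2.4.1 makes the primary outcome the frequency and character of adverse events at 48 hours, with no relatedness condition.
- Table 1 in section 3.1 has a row "Any other adverse event" for Day 0 and Day 2.
- Sections 5.2.3 and 5.2.5 refer to any adverse events.
- The secondary outcome in the Study Summary is "Any other adverse event associated with the patch test application" of the salve. The objective in 2.3.1 also uses 'associated'.

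On causality, section 3.4 states: "The causality of SAEs (i.e. relationship to trial intervention) will be assessed by the investigator(s) using the SAE form". That form uses the five-level scale of Table 2. Section 3.5 separately gives co-investigators the task of assigning seriousness, causality and expectedness by clinical judgement, and does not limit it to serious events.

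**The concern.** The objective is a frequency of adverse events, so the rule for what enters the record determines the result. Three scopes stand side by side: any event, events associated with the patch test, and events related to the salve. Staff who follow 3.3.1 and staff who follow Table 1 or 5.2.3 could record different events for the same volunteer.

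The narrowest scope needs an attribution that this design supports poorly. Section 1.8 names both the salve and the sticking plaster as possible sources of a skin reaction. There is no comparator arm (2.9.1) and no blinding (2.11). Because unexpected AEs come by self-report, the participant may be the first to judge whether an event counts as related. An event left out at that stage cannot be recovered by any later analysis plan.

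**Working it through.** The protocol gives no AE rate, no sample size calculation and no figure to reproduce. The check is therefore mainly a comparison of passages.

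**Step 1. Which events does each section admit?**

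| Place | Scope | Relatedness condition |
|---|---|---|
| 3.3.1, definition | any untoward occurrence | none |
| 3.3.1, symptom capture after the expected list | symptoms within and at 48 hours | none stated |
| 3.3.1, unexpected AEs | unexpected events | related to the salve |
| 2.4.1, primary outcome | adverse events at 48 hours | none |
| Table 1 | any other adverse event | none |
| 5.2.3 and 5.2.5 | any adverse events | none |
| Study Summary (secondary), 2.3.1 | adverse events | associated with the patch test |
| 3.4, serious events | all SAEs to 48 hours | none for recording |

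The third row is the only one that ties recording to the salve. Serious events are recorded whatever their cause, so the conflict concerns non-serious unexpected events.

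**Step 2. Follow kinds of event through the text.**

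- *Redness, itchiness, discomfort.* The expected list is introduced as related to the intervention, but the sentence on capture asks for no attribution. Section 2.2 also has participants asked about any sign of skin reaction. These events are recorded.
- *Heat, swelling or another skin effect.* Section 5.1 counts these in the primary outcome, but 3.3.1 does not list them as expected. Its list is open-ended, and the question in 2.2 should elicit them. Read literally, however, the unexpected-AE sentence can apply to them.
- *Swelling attributed to the plaster.* This is associated with the patch test (2.3.1) but not related to the salve (3.3.1), so the two wordings give different answers.
- *A non-skin event.* Table 1 and 5.2.3 admit it. The unexpected-AE sentence admits it only if someone judges it related.

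**Step 3. How is relatedness decided for a non-serious event?** Table 2 is attached to the SAE form. Section 3.5, item 2, gives the judgement to co-investigators but names no scale, and it does not require events judged unrelated to be kept. Item 4 there requires AE recording in line with the protocol, which leads back to 3.3.1.

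**Step 4. Direction, with an illustration on assumed inputs.** Let p be the true proportion of volunteers with an unexpected event and s the share of those volunteers whose event is kept. Recorded frequency is p × s, which cannot exceed p. The chance of recording none among n volunteers is (1 − p × s)^n. The protocol gives n = 90 to 100 and no value for p or s. For n = 100:

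| Assumed p | s = 1 | s = 0.75 | s = 0.5 | s = 0.25 |
|---|---|---|---|---|
| 2% | 13.3% | 22.1% | 36.6% | 60.6% |
| 5% | 0.6% | 2.2% | 8.0% | 28.4% |
| 10% | 0.003% | 0.04% | 0.6% | 8.0% |

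For example, with p = 5% and s = 0.5: (1 − 0.025)^100 = 0.080. With n = 90 the 5% row reads 1.0%, 3.2%, 10.2% and 32.2%.

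If no unexpected event is recorded, the one-sided 95% upper bound is 1 − 0.05^(1/n), which is 3.0% for n = 100 and 3.3% for n = 90. That bound applies to p × s, not to p. These figures show the direction and form of the effect and do not estimate it.

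**The case against.** The strongest reply is that the disputed sentence says how and when unexpected AEs are recorded, not that others are discarded; the word 'only' does not appear in it. Section 2.4.1, Table 1, 5.2.3, 5.2.5 and item 4 of 3.5 all provide for AEs without a relatedness condition. The word 'associated' refers to the patch test and may mean no more than occurring with it. The case report forms exist but are not shown, and they may collect everything.

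Most of this stands. It shows an unreconciled inconsistency rather than a settled exclusion rule. It does not remove the conflict, because item 4 of 3.5 defers to the protocol's own requirements.

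Two stronger readings are tempting, and the document does not support them:

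- A reader might infer that the study's main count passes through a relatedness filter. The Study Summary's primary outcome is skin irritation. The listed skin symptoms are captured without attribution, and 2.2 asks about any skin reaction. Most of the primary count is untouched.
- A reader might infer that relatedness is assessed only for serious events. Item 2 of 3.5 assigns causality without that limit; only the Table 2 scale and form are specific to serious events.

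Nor does the protocol's stated confidence in the product's safety show that staff would call reactions unrelated. That would be speculation about motive.

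**Conclusion.** The point holds as an inconsistency in the recording rule, with limited reach. One sentence of 3.3.1 conflicts with the definition in the same section and with 2.4.1, Table 1, 5.2.3 and 5.2.5, while the Study Summary and 2.3.1 add a third scope. No scale is set for relatedness of non-serious events.

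The exposed events are unexpected and non-serious: mainly non-skin events, possibly heat, swelling or other skin effects, and more broadly whatever falls under the wide primary outcome of 2.4.1. Measured against an all-cause frequency, any loss is downward and irreversible. Its size cannot be estimated, since the protocol gives neither an event rate nor a share that would be judged unrelated. The conclusion assumes that staff might follow 3.3.1 literally; if the forms already collect every event, only the wording needs repair. It is worth correcting before recruitment because this is a data-capture rule that a later analysis plan could not mend.

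**What to change.** In 3.3.1, delete the condition tying unexpected AEs to the salve, and state that every AE from plaster application to the 48-hour contact is recorded, whatever its presumed cause or expectedness. Hold relatedness as a separate attribute for all AEs, using the existing Table 2 scale, so that events judged unrelated stay in the data. Align the secondary outcome in the Study Summary and the objective in 2.3.1 with that scope. How all-cause and related frequencies are then presented can be left to the analysis plan.

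The cost is a few sentences and one extra field per event on the case report form. The small downside is that some unrelated background events will appear in the all-cause count; the relatedness field lets a reader set them aside.
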